7.13 Study Schedule of Activities

Assessments	Screening/Baseline	Training / Day 0	Week 1 (Phone Call)	Week 4	Week 8	Week 12	Week 18 (Phone call)	Week 24	Week 32 (Phone call)	Week 40 (Phone call)	Week 52
Visit Window	N/A	N/A	+7 Days	±7 Days	±7 days	±7 days	±14 days	±14days	±14 days	±14 days	±14 days
Informed Consent	X										
Inclusion/Exclusion	X										
Demographics	X										
Medical History/Status	X ¹										
Vital Signs² (Height, Weight)	X			X	X	X		X			X
Skin Assessment	X			X	X	X		X			X
Limb Circumference	X			X	X	X		X			X
Photograph (Leg)	X			X	X	X		X			X
Prescribed Care & Treatment Protocol	X		X	X	X	X	X	X	X	X	X
Medication Review	X		X	X	X	X	X	X	X	X	X
Quality of Life Assessments	X					X		X			X
Subject Diary	X ³			X	X	X		X			X
Flexitouch Compliance			X	X	X	X	X	X	X	X	X
HCU, Adverse Events, & Device Observations			X	X	X	X	X	X	X	X	X
Flexitouch Training		X									

¹Includes Lymphedema History

²Height and weight collected at Screening/Baseline, weight collected at all subsequent visits

³Dispense and train subject on subject diary completion

8.0 Study Device Accountability

To participate in the study, the Flexitouch must be covered by a payer. The Flexitouch will be provided to the subject and tracked according to normal business practices. Subjects' whose payer requires rental of the Flexitouch will be excluded from the study.

9.0 Risk Analysis and Adverse Events

9.1 Risk Analysis

This study does not present risks above and beyond those normally associated with the use of this market cleared product. Pneumatic compression is a minimal risk therapy with minimal known complications or adverse events. However, as with any treatment, there is the possibility of undesirable events such as a local skin reaction to the device materials. The subject will be made aware of known complications at time of consent and monitored closely throughout the study.

Study subjects will be informed of any significant new findings that develop during the course of this study that may affect their willingness to continue participation. The principal investigator will oversee all safety aspects of the study and report all adverse events to the IRB per the IRB's reporting requirements. Should a subject choose to terminate his or her participation in the study, they will be treated according to the standard of care that applies at the point of withdrawal.

9.2 Adverse Events

This study will collect device-related adverse events. A device related adverse event is defined as any untoward medical occurrence in a subject that is associated with the use of the Flexitouch device. If this device-related event is serious, investigators must report the event to Tactile Medical within 72 hours and to their IRB per their policy. A serious adverse event is defined as an event that, 1) results in death; 2) is life-threatening (places the subject at immediate risk of death from the experience as it occurred; 3) results in a persistent or significant disability/incapacity (substantial disruption of one's ability to carry out normal life functions); 4) results in medical or surgical intervention; 5) results in or prolongs existing hospitalization; 6) is medically unexpected, regardless of severity.

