5.2.3 Subject Withdrawal or Early Termination

Subjects will exit the study if they meet any of the following criteria:

- Subject death
- Subject voluntarily withdraws
- Subject acquires one or more of the exclusion criteria whereby the investigator deems study discontinuation a necessity
 - If subject acquires an infection, they may be treated for the infection and continue in the trial at the investigator’s discretion. Detailed information regarding the infection, nature, treatment, and duration will be recorded.
- Subject diary shows an unwillingness to remain partially compliant or compliant with prescribed care (subject will be considered a screen failure if he or she uses the device <3 times per week on average at the Week 4 visit).

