6.2 Week 0/Training

- The subject will receive the Flexitouch system or Flexitouch Plus and be instructed on use from a Tactile Medical trainer. Device treatment will commence following the visit from the trainer.

6.3 Weeks 1 (+7 days), 18, 32, & 40 (± 14 days) Follow-up Phone Calls

- Prescribed care and treatment protocol
- Medication review
- Flexitouch compliance assessment
- Complication, adverse event, and device observation assessment

6.4 Weeks 4, 8, 12 (± 7 days), 24, and 52 (± 14 days) In-Clinic Follow-Up Visit(s)

- Weight (kg)
- Skin assessment
- Limb circumference
- Photographs (Leg)
- Prescribed care and treatment protocol
- Medication review
- QoL Questionnaires (Weeks 12, 24, and 52 only)
 - LYMQOL
 - SF-36
- Subject diary collection
- Flexitouch compliance assessment
- Complication, adverse event, and device observation assessment

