7.8 Medication Review

At each clinic visit, use of the following medications will be documented:

- Beta blockers
- Diuretics
- Oral steroids
- Non-Steroidal Anti-Inflammatory Drugs (NSAIDs)

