7.11.2 Device-Related Adverse Events

Any untoward medical occurrence in a subject that is associated with the use of the Flexitouch device.

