11.4 Data Safety Monitoring

A periodic review may be completed by a designated member of the Scientific Advisory Board. The frequency of the review will be determined on a number of parameters including but not limited to: the rate of enrollment, number of complications, and number of significant deviations from the protocol. At the conclusion of the review the reviewer may provide recommendations that pertaining to study continuation, modification or termination of the trial, or a specific investigational site.

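### Adverse events are recorded only if attributed to the device, and the complications that the protocol says it will assess and count have no definition and no specified record

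*Combined protocol and SAP*

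**What the plan says.** Section 9.2 sets the scope: "This study will collect device-related adverse events". Section 7.11.2 defines these events as "Any untoward medical occurrence in a subject that is associated with the use of the Flexitouch device". Expedited reporting carries the same condition: "If this device-related event is serious, investigators must report the event to Tactile Medical within 72 hours". Neither section says who judges association, on what scale or by what criteria.

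Other parts of the protocol speak more widely:

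- The synopsis lists a rate of lymphedema- and vein-related complications among the primary endpoints, separately from unscheduled visits. Section 4.0 repeats both. Section 5.1.1 lists health care utilization (HCU) instead.
- Sections 6.3 and 6.4 include "Complication, adverse event, and device observation assessment" at each follow-up call and clinic visit.
- Section 11.4 lets the frequency of the safety review depend partly on the "number of complications".
- Section 9.1 has the principal investigator "report all adverse events to the IRB", subject to the IRB's own requirements.
- Section 7.10 gives active infection and DVT as examples of complications that interrupt device use.

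Section 7.11 and the schedule in 7.13 provide for three kinds of record in follow-up: HCU, adverse events (device-related, per 7.11.2) and device observations. Two routes do not depend on attribution to the device. For infection, section 5.2.3 states: "Detailed information regarding the infection, nature, treatment, and duration will be recorded". Section 7.11.1 covers all lymphedema- and vein-related visits, whatever their relation to the device.

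**The concern.** The attribution filter acts before an event is recorded. An event that the site puts down to the underlying disease does not enter the adverse event or serious adverse event data. Section 3.1 itself describes lymphedematous limbs as prone to skin breakdown and repeated infection, so a site has a ready alternative explanation for cellulitis. With one arm there is no comparator rate against which to judge whether attribution was reasonable.

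Two stated uses of the data are affected. The synopsis names a complication rate as a primary endpoint, and the 11.4 review relies on a complication count. Neither has a defined numerator. Section 7.10 also has a subject withdrawn when a complication prevents four continuous weeks of treatment before the final clinic visit. Complications can therefore remove subjects from follow-up, although the text does not say how a complication is identified and logged.

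**Working it through.** The documents state no expected event rate, attribution share or safety precision, so there is no plan figure to reproduce. The main check is textual: for each type of event, is there a route into the study data that does not need attribution to the device?

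| Event | Where the protocol names it | Route without attribution | Clean event count? |
|---|---|---|---|
| Infection | 5.2.2 (exclusion), 5.2.3, 7.10 | Details recorded under 5.2.3; visits under HCU if lymphedema-related | No: 5.2.3 has no matching item in 7.11 or the schedule, and HCU counts visits |
| DVT | 5.2.2 (exclusion), 7.10 | Visit under HCU, if vein-related | No: 7.11.1 asks for visits, not diagnoses, and one event may lead to several visits |
| PE | 5.2.2 only | HCU, only if its care is classed as vein-related, which 7.11.1 does not settle | No |
| Pulmonary edema, decompensated heart failure | 5.2.2 only | None assured | No |
| Death | 5.2.3, 9.2 | Study exit under 5.2.3 | The exit is known; no cause field is specified |

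Section 7.8 offers little cross-check. It says that "use of the following medications will be documented" and lists beta blockers, diuretics, oral steroids and NSAIDs. Antibiotics and anticoagulants, which could point to an infection or a DVT, are not listed.

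An illustration shows how the filter acts on an event with no other route. It should not be applied to infection or DVT, which are partly captured elsewhere.

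Inputs: N = 300 (section 13.2, an upper limit); 52-week risk p and share attributed to the device a, both **assumed**, since the documents give neither.

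Expected events = N × p. Expected recorded = N × p × a. P(none recorded) = (1 − p × a)^300.

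| p | Expected events | Expected recorded at a = 10 / 25 / 50% | P(none recorded) at a = 10 / 25 / 50% | P(none) if all are recorded |
|---|---|---|---|---|
| 1% | 3 | 0.3 / 0.75 / 1.5 | 0.74 / 0.47 / 0.22 | 0.05 |
| 3% | 9 | 0.9 / 2.25 / 4.5 | 0.41 / 0.10 / 0.01 | <0.001 |
| 5% | 15 | 1.5 / 3.75 / 7.5 | 0.22 / 0.02 / <0.001 | <0.001 |

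For example, at p = 1% and a = 10%: 300 × 0.01 × 0.10 = 0.3, and (1 − 0.001)^300 = 0.74. At a = 100% nothing is lost. An empty adverse event table is a realistic outcome only for rare events or low attribution; for commoner events the effect is a reduced count.

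**The case against.** The strongest reply is that this is a post-market, on-label, observational study of a cleared device. Device-related collection is an openly stated scope, and no objective or endpoint promises an all-cause harm rate. That stands: a rate labelled device-related is narrower than an all-cause rate, not wrong.

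A reader might infer that infection and DVT are lost altogether. The documents do not support that. Infection details are to be recorded with no attribution condition. The sentence follows one about subjects who continue, but it does not limit itself to them. Vein-related visits enter HCU whether or not the device is blamed. What remains is that neither route yields a count of diagnosed events.

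A reader might also treat PE and acute heart failure as harms that the protocol ascribes to the device. It names them only as exclusion conditions; the example in the risk analysis (9.1) is a local skin reaction.

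The case report forms are not in the documents, so a complication field may exist. Source records are kept for at least ten years (11.5) and monitors have direct access to source data (11.3), so a chart review could recover events. Both points stand. They limit the claim to what the text specifies and to what the study dataset can show.

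The clash between 9.1 and 9.2 is milder than it looks, because the 9.1 sentence concerns IRB reporting under IRB rules. It still speaks of all adverse events where 9.2 collects a subset.

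Finally, HCU might be meant to stand for the complication rate. The synopsis and section 4.0 list complications and unscheduled visits as separate items, so one visit count cannot serve as both.

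**Conclusion.** The point holds in this form. Capture of adverse and serious adverse events depends on site attribution by no stated method. The complications that the synopsis, the objectives, sections 6.3 and 6.4 and section 11.4 rely on are not defined and have no specified record. Infection and DVT are partly captured but have no clean event count. PE has a route only if it is classed as vein-related HCU. Acute heart failure or pulmonary edema judged unrelated has none.

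The all-cause rate may therefore be understated. The documents give no event rates and no attribution share, so the size cannot be estimated, and the tabulated figures only show the mechanism under assumed values. That sites will tend to blame the disease is plausible but not shown. With a single arm, the attribution cannot be checked from the study dataset.

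**What to change.** In sections 7.11 and 9.2:

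1. Define complication as a short fixed list drawn from the protocol's own terms: infection, thrombophlebitis, DVT, PE, pulmonary edema, decompensated heart failure and death.
2. Record every follow-up occurrence regardless of cause, with onset date, device-use status at onset and relatedness as separate fields. State who judges relatedness and by what criteria.
3. Report all-cause and device-attributed rates side by side, and use the all-cause count as the number of complications in 11.4.
4. Reconcile the wording on all adverse events in 9.1 with that on device-related events in 9.2, and the complication rate in the synopsis and section 4.0 with section 5.1.1.

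Device-related collection can stay for everything outside the list. Adding antibiotics and anticoagulants to the 7.8 list is an optional cross-check.

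The contacts are already scheduled, so no visit or test is added. The cost is a few more form entries, and the reported event rate will be higher than under the present rule.

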11.5 Reports and Records

Records to be maintained by the investigator in a designated study file include:

- Investigational plan and all amendments
- Signed Investigator Agreement/Research Contract
- IRB approval letter, including a copy of the approved consent forms, progress reports, Adverse Event Report
- IRB roster or Assurance number, if applicable
- All correspondences relating to the conduct of this study between the site and sponsor, IRBs, and study monitor
- Curriculum Vitae and professional license for all study personnel, if applicable
- Site personnel signature and documentation regarding the Investigator's delegation of responsibility
- Clinical Site Visit log
- Protocol/device related training records for all applicable study personnel
- Screening log
- Reports (Table 4)

The following records must be maintained for each subject enrolled:

- Signed and dated informed consent forms
- Completed CRFs, queries, and source document worksheets (if applicable)
- Complete medical records including procedure reports, lab reports (as applicable), etc.

Investigators are required to prepare and submit to Tactile Medical or its designees complete, accurate, and timely reports on this investigation as required by regulations. The types of reports to be submitted are summarized in the table below.

Table 4: Investigator Reports

Reports	Submit To	Timeframe
Serious Adverse Event (SAE)	Sponsor and Reviewing IRB	Sponsor: 72 hours IRB: per their procedure
Withdrawal of IRB Approval	Sponsor	Within 5 working Days
Progress	Sponsor and Reviewing IRB	Annually, at a minimum
Final	Sponsor and Reviewing IRB	Within 3 months following the completion or termination of the Investigator's part

Subject study records, correspondence files, all supporting study documentation, and reports must remain on file at the investigational site for a minimum of ten years after the conclusion of this study. All investigators must contact Tactile Medical personnel prior to destroying or archiving off-site any records and reports pertaining to this study to ensure that they no longer need to be retained on-site. Additionally, Tactile Medical personnel must be contacted if the Investigator plans to leave the investigational site to ensure that arrangements for a new Investigator or records transfer are made prior to the Investigator's departure.

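### Two of the six criteria in 9.2 make a device-related event serious with no severity threshold, so any SAE listing would mix serious harm with minor events that were treated or judged unexpected

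*Combined protocol and SAP*

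**What the plan says.** Section 9.2 sets the scope first: "This study will collect device-related adverse events". It then gives the reporting duty: "If this device-related event is serious, investigators must report the event to Tactile Medical within 72 hours and to their IRB per their policy". The definition of serious follows as six numbered alternatives. Death and immediate threat to life are the first two. The third is "3) results in a persistent or significant disability/incapacity (substantial disruption of one's ability to carry out normal life functions". The remaining three are "4) results in medical or surgical intervention; 5) results in or prolongs existing hospitalization; 6) is medically unexpected, regardless of severity".

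Section 9.1 describes pneumatic compression as a low-risk therapy and gives one example of harm: "there is the possibility of undesirable events such as a local skin reaction to the device materials". It adds that subjects are told of known complications at consent. Table 4 in 11.5 repeats the 72-hour timeline for SAEs and gives no definition of its own.

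**The concern.** Seriousness should classify an event by how much harm it did or threatened. Criteria 4 and 6 classify it by other things: whether someone intervened, and whether the event was foreseen. Because any one criterion is enough, a trivial event can qualify through either of them.

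This matters because the serious/non-serious flag is the only severity-type classification of device harm in the protocol. If it is blurred, nothing else in the text separates the grave from the minor. A reader of a later SAE table could not tell whether a given total reflects admissions or treated skin irritation. Sites may also differ in what they call an intervention or unexpected, so the total could vary with how literally each site reads the rule.

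Minor complaints are likely to surface. Section 7.10 has sites ask about pain or discomfort during device use at every follow-up contact. There are nine of these in the schedule: four calls (weeks 1, 18, 32, 40) plus five visits (weeks 4, 8, 12, 24, 52). Section 7.4.2 has skin changes, including dermatitis and blisters, checked at each clinic visit.

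**Working it through.** The plan states no SAE rate, threshold or power figure, so there is nothing numeric to reproduce. Section 13.2 gives a convenience sample of up to 300. The check is a literal reading of the definition.

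**Step 1. What each criterion requires (9.2).**

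| Criterion | What is enough | Threshold of harm |
|---|---|---|
| 1 | Death | Yes |
| 2 | Immediate risk of death | Yes |
| 3 | Lasting or significant disability | Yes |
| 4 | Any medical or surgical intervention | None stated |
| 5 | Hospital admission or a longer stay | Yes |
| 6 | Being unexpected | Expressly set aside |

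Criterion 6 says so in terms: "6) is medically unexpected, regardless of severity". For criterion 4 the absence of a threshold follows from the missing qualifier; the text does not say severity is irrelevant there.

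**Step 2. Is there a qualifier elsewhere?** Section 7.11.2 defines a device-related adverse event without grading it. Section 9.1 gives an example and no scale. Table 4 gives timelines only. The grades in 7.4.1 and the stages in 7.4.3 describe fibrosis and lymphedema, not adverse events. So nothing narrows criteria 4 and 6.

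**Step 3. Apply the rule to four simple cases.**

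- (a) Minor device-related skin reaction, medically treated: meets criterion 4, so serious.
- (b) Minor device-related event, untreated, judged medically unexpected: meets criterion 6, so serious.
- (c) Minor skin reaction of the kind foreseen in 9.1, untreated: meets none of the six, so not serious.
- (d) Event unrelated to the device: outside what 9.2 collects.

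Cases (a) and (b) show the defect. Case (c) shows its limit.

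**Step 4. What depends on the label?** In the documents it triggers the 72-hour report to the sponsor and a report to the IRB under the IRB's own policy (9.2, Table 4). It does not appear in the primary endpoints (5.1.1), the secondary endpoints (5.1.2), the statistical section (13.1) or the sample size (13.2). The review in 11.4 is optional; among the parameters that set its frequency, it names complications and not SAEs.

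**Step 5. Can the mixture be undone afterwards?** Yes, if the criterion met is recorded for each event, because criteria 1–3 and 5 still mark severe outcomes. The protocol does not require that record.

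**The case against.** The best defence is that the definition is deliberately cautious. It errs toward more reporting in a post-market, on-label study, and narrowing it could cost the sponsor early notice of some events. The caution is legitimate, and the loss of notice would be real if criterion 4 were simply cut back: treated, foreseen events would drop out of the 72-hour stream. That is a reason to separate the label from the reporting duty. It does not justify calling minor events serious.

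Several stronger readings are tempting, and the documents do not support them.

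- *Minor skin reactions in general become SAEs.* They do not. An untreated one of the foreseen kind meets no criterion. Nor does nearly every device-related event qualify; only those treated, judged unexpected or severe do.
- *Whatever 9.1 does not name is unexpected.* Section 9.1 offers an example, not a closed list, and refers to known complications disclosed at consent. The consent pages are not in the text supplied, so a fuller list cannot be ruled out. Section 7.10 also anticipates discomfort, infection and DVT.
- *The study's main safety result or its safety review is distorted.* No SAE rate is a planned endpoint or analysis, and 11.4 does not rest on an SAE count.
- *Table 4 and 9.2 require different sets of events to be reported.* This is weak. Section 9.2 collects only device-related events, and Table 4 is a summary of timelines that does not widen collection. It lacks one clarifying word.
- *The excess can be put at some number of SAEs.* Suppose 10–20% of 300 subjects had one minor event and 30–70% of those were treated or unexpected. The result would be 300 × 0.10 × 0.30 = 9 to 300 × 0.20 × 0.70 = 42. Neither range has any basis in the documents, and 9.1 expects few complications. The figure only returns its assumptions.

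**Conclusion.** The concern holds in a limited form. Read as written, criteria 4 and 6 classify minor device-related events as serious when they are treated or judged unexpected, and no other part of the protocol restores the distinction. The consequence is 72-hour reports in which minor and grave events share one label, and the same mixture in any SAE listing or total published later.

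The size cannot be stated as a count, because the documents give no rate of device-related events and no share that is treated or unexpected. There is no effect on endpoints, sample size or stopping rules. The point is worth correcting because this is the protocol's only rule for seriousness and the correction is cheap, but it does not threaten the study's planned conclusions.

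The conclusion rests on two assumptions: that sites apply the six criteria literally as alternatives, and that the CRF, which is not in the documents, does not already record severity or the criterion met. If it does, the separation is recoverable and the point reduces to wording.

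**What to change.** In 9.2:

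1. Limit criterion 4 to intervention needed to prevent an outcome of the kind in criteria 1–3 or 5.
2. Remove criterion 6 from the definition of serious and record it as a separate unanticipated yes/no field.
3. Keep the 72-hour sponsor report for every event that triggers it now, including treated and unanticipated events that are no longer labelled serious. Say so in Table 4 as well, since its SAE row would otherwise shrink with the label. The reported set is then unchanged: the narrowed criterion 4 lies inside the present one, so revised SAEs plus all treated and all unanticipated device-related events equal the union of the six present criteria.
4. Record the criterion met for each event.
5. Report SAEs separately from treated or unanticipated non-serious device-related events.

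Optionally, add the words device-related to the SAE row of Table 4 to make the scope plain.

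The cost is a few sentences in 9.2 and Table 4, one or two CRF fields, brief site retraining, and reclassification of events already reported. No expedited information is lost.
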